7.7 Blinding and unblinding methods

- Bottles containing study medication for individual patients will not be labelled with any information to indicate whether the capsules are YF476 or placebo.
- Patients will be blinded to study treatment.
- One member of the HMR Statistics and Data Management Department will not be blinded. That person will generate the randomization code. The Columbia University biostatistician will be blinded.
- All Investigators will be blinded to study treatment.

-
- For each site, there will be a blinded monitor and an unblinded monitor. The unblinded monitor will review dispensing records at the site Pharmacy.
 - Pharmacy staff will not be blinded.
 - The Data and Safety Monitoring Board will not be blinded.
 - The blind will be broken by the investigator or delegate in the following circumstances:
 - If unblinding is required in the interest of the safety of a subject, an investigator will discuss the matter with the sponsor before opening the individual code-break envelope for that subject. In a medical emergency, the principal investigator or delegate may open the individual code-break envelope for that subject without prior consultation with the sponsor. In that event, the principal investigator or delegate will notify the sponsor as soon as possible that the randomisation code has been broken for the subject.
 - The blind will be broken for the entire study population at the completion of the study, after the statistical analysis plan (SAP) has been signed and the database has been locked.

7.8 YF476 destruction/disposal

At the completion of investigation, the site Pharmacy will return all unused YF476 and placebo capsules to the HMR Pharmacy.

8 Clinical evaluations and procedures

8.1 Schedule of events

Evaluation/ Procedure	Baseline Testing/ Prestudy Evaluation		Study treatment		Follow-up period
	Visit 1 ¹	Visit 2	Week 6 visit	Week 12 visit	Follow-up
	Registration	Randomization, & Endoscopy	Week 6	Week 12	Follow Up Visit 4 weeks after stopping treatment
Informed consent	X				
Assess eligibility	X				
Central pathology review ²	X				
Medical history	X				
Physical exam	X				
Vital signs	X	X ⁵	X	X	X
Height and weight/ waist circumference	X				
Smoking history	X				
Medication history	X				
Blood and urine collection for safety tests	X	X ⁵	X	X	X
Urine pregnancy test ⁴	X	X ⁵	X	X	X
ECG	X	X ⁵	X	X	X
Blood for YF476 assay ³			X	X	
Blood for assay of fasting serum gastrin and plasma CgA, and serum for storage		X	X	X	X
EGD (Upper GI endoscopy)		X		X	
Biopsies		X		X	
Concomitant medication assessment		X	X	X	
Dispense study medication		X	X		
Collect study medication			X	X	
Compliance assessment			X	X	
AE assessment		X	X	X	X

1. There may be up to a 2-week gap between Visits 1 and 2.
2. Review of patient's history to obtain histological confirmation of the patient's eligibility to participate in the trial.
3. Plasma YF476 assay: patients fast overnight. For the Week 6 and 12 visits, patients bring their container of study medication with them, and take study medication only after collection of blood samples for trough YF476, fasting serum gastrin and CgA levels, and endoscopy (if applicable). Patients stay for 1 h after dosing for collection of a blood sample for peak YF476 level.
4. Pre-menopausal women only.
5. These tests may be omitted if Visit 2 occurs on the same day as Visit 1.

8.2 Baseline testing and pre-study evaluation

Visit 1: registration

Patients will attend the clinic and complete the informed consent form. The investigator will complete the following evaluation for each patient, and enter the data from this visit, and all subsequent visits, on the appropriate page of the CRF:

- review of most recent endoscopy (within 3 years) to confirm diagnosis of Barrett's esophagus with no dysplasia;
- review of medication history to determine that participants meet the inclusion criteria (daily PPI use for at least the most recent 12 months before study entry, and stable PPI dose for at least the most recent 3 months before study entry);
- medical history, physical examination, ECG and vital signs;
- blood and urine samples for laboratory safety tests; and
- urine pregnancy test (pre-menopausal women only).

Visit 2: baseline

Visit 2 may occur on the same day or up to 2 weeks after Visit 1. The patient will fast for 6 hours before the study visit. The investigator will complete the following evaluation for each patient, and enter the data from this visit, and all subsequent visits, on the appropriate page of the CRF. If Visits 1 and 2 are combined, only 1 blood sample (safety tests, fasting serum gastrin, plasma CgA and serum for storage) and 1 urine sample will be taken, and ECG, vital signs and pregnancy tests will be done only once.

- blood and urine samples for laboratory safety tests, urine pregnancy test (pre-menopausal women only), ECG and vital signs;
- blood samples for fasting serum gastrin, plasma CgA and serum for storage;
- endoscopy and biopsies; and
- randomization to 25 mg YF476 or placebo, and dispensing of study medication (a 42-day supply, plus overage: 1 bottle of 25 mg YF476 or placebo containing 46 capsules).

The investigator will then:

- give the patient a diary card;
- tell the patient to start taking their study medication the day after Visit 2;
- remind the patient to fast before the Week 6 visit (6 weeks after starting study medication); and
- remind the patient not to take their study medication at home on the day of the Week 6 visit, but instead to bring their container of study medication with them to the visit, and take their dose at the clinic, after the fasting blood tests.

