1.2 Trial medication

YF476 (25 mg) or matching placebo: one capsule to be taken by mouth once daily for 12 weeks. Study medication will be taken with breakfast except on clinic visit days, when patients will fast overnight and take study medication after completion of study procedures.

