8.5 Post-treatment follow-up period

Follow-up: 4 weeks after stopping study treatment

The patient will return 4 weeks after the end of the treatment period. The investigator will:

- assess the patient for any delayed adverse events;
- do an ECG and vital signs;
- take blood and urine for laboratory safety tests and urine pregnancy testing (premenopausal women only); and
- take blood samples for fasting serum gastrin, plasma CgA, and serum for storage.

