### 4.2.2 Secondary Endpoints

- Biomarkers
  - Change from baseline at Week 12 in biomarkers potentially associated with esophageal adenocarcinoma, in particular:
    - Change in CCK2R mRNA levels (measured by qRT-PCR)
    - Change in DCAMKL1 expression (measured by IHC)
    - Change in DCAMKL1 mRNA levels (qRT-PCR)
    - Change in COX-2 mRNA levels (qRT-PCR)
    - Change in p53 expression (IHC)
  - Gene expression will be measured using RNA-Seq. Further examination of any changes in expression from baseline may be done using qRT-PCR and IHC
  - Reduction in PPI-induced increase in plasma CgA
  - Increase in PPI-induced hypergastrinaemia
- Safety
  - Vital signs, ECG, physical examination, laboratory safety tests: blood tests: red blood cells (RBC), haemoglobin, haematocrit, platelets, white blood cells (WBC, differential: neutrophils, bands, lymphocytes, monocytes, eosinophils, basophils), sodium, potassium, magnesium, chloride, bicarbonate, creatinine, serum glucose, blood urea nitrogen (BUN), alkaline phosphatase, lactate dehydrogenase (LDH), serum glutamic-oxaloacetic transaminase/aspartate amino transferase (SGOT/AST), serum glutamicpyruvic transaminase/ alanine aminotransferase (SGPT/ALT), total bilirubin, total protein, albumin, calcium, amylase, lipase; and urine tests: pH, specific gravity, protein, glucose, ketones, blood.
  - Change in histology
- Tolerability: assessment of adverse events.
- Pharmacokinetics: trough and peak concentration of netazepide

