## **15 Efficacy Analyses**

Efficacy data (serum gastrin and CgA) will be summarised using the ITT and PP populations. Summaries based on the PP population will only be produced if there is a difference between the ITT and PP populations

Serum gastrin and plasma CgA data at each planned visit, and change in Serum gastrin and plasma CgA from baseline at each planned post-baseline visit, will be summarised by treatment group and visit. Individual values will be presented by patient

Mean profile plots for serum gastrin and CgA will also be produced. Each plot will contain all results for all subjects in the active and placebo arms

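### The fast before gastrin and CgA sampling is 6 hours at baseline, overnight at Weeks 6 and 12, and of no stated length at follow-up, so each arm's change from baseline can carry a fasting component

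*Protocol*

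**What the plan says.** Fasting is part of the endpoint: the secondary objectives (protocol 1.3 and 2.2) name fasting serum gastrin, together with plasma CgA. Four samples are planned, at Visit 2, Week 6, Week 12 and follow-up (protocol 8.1).

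- **Visit 2.** Protocol 8.2 states "The patient will fast for 6 hours before the study visit" and lists "blood samples for fasting serum gastrin, plasma CgA and serum for storage" among the procedures. It lists no check of the fast.
- **Weeks 6 and 12.** Schedule footnote 3 says "Plasma YF476 assay: patients fast overnight", and it covers the gastrin and CgA samples taken before the dose. Protocol 1.2 describes clinic days as those "when patients will fast overnight and take study medication after completion of study procedures". Sections 8.3 and 8.4 have the site check fasting status, without naming a duration.
- **Follow-up.** Protocol 8.5 tells the site to "take blood samples for fasting serum gastrin, plasma CgA, and serum for storage". It gives no duration and no check, and 8.4 has no reminder to fast before this visit. Sections 8.2 and 8.3 do give such a reminder for Weeks 6 and 12.
- **General rule.** Protocol 10.3.2, under safety blood tests, says blood is drawn fasting but sets no duration.

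On analysis, SAP 15 says that "change in Serum gastrin and plasma CgA from baseline at each planned post-baseline visit, will be summarised by treatment group and visit", with mean profile plots. One of the SAP 4.2.2 endpoints is worded "Increase in PPI-induced hypergastrinaemia". Protocol 13.4 also plans a correlation of baseline gastrin with the later Ki67 change.

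**The concern.** A change from baseline is clean only if both values are measured under the same conditions. Here the written condition differs between the baseline and the values from which it is subtracted. By calling for fasting samples, the protocol treats food as something that can affect the measurement. A patient who eats in the morning and has an afternoon endoscopy would satisfy the 6-hour rule at Visit 2 but not the overnight rule at Week 12.

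Three things are at stake:

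- If a shorter fast raises the baseline value, the change within each arm is pushed downwards. A real rise in gastrin then looks smaller than it is, and a fall can appear where there is none. A short fast at follow-up would act in the opposite direction.
- If only some patients have the shorter fast, the change becomes more variable, with about 10 patients per arm.
- The same variability enters baseline gastrin as a predictor of the Ki67 change and would tend to dilute the correlation.

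The endpoints are worded as an increase in gastrin and a reduction in CgA, which invites reading each arm on its own.

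**Working it through.** **1. The sections side by side**

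| Visit | Written fast | Reminder at the visit before | Check on the day |
|---|---|---|---|
| Visit 2 | 6 hours (8.2) | none listed | none listed |
| Week 6 | overnight (1.2; 8.1 footnote 3) | yes (8.2) | yes, no duration (8.3) |
| Week 12 | overnight (1.2; 8.1 footnote 3) | yes (8.3) | yes, no duration (8.4) |
| Follow-up | labelled fasting, no duration (8.1, 8.5) | none (8.4) | none (8.5) |

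Section 1.2 does not settle the baseline. Its sentence concerns days on which study medication is taken, and the first dose is the day after Visit 2 (1.6, 8.2). Follow-up is not a minor visit for this purpose: 13.4 lists the gastrin and CgA change to Visit 5, which is follow-up by the five-visit count in 4.1, although 1.9 gives Week 12.

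**2. The plan's own figure**

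The only power statement is for Ki67 (protocol 13.7, SAP 8.1). It uses a two-sample t-test with 10 per arm, 18 degrees of freedom and two-sided 0.05. The noncentrality is difference / (SD × √(2/10)).

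- 30% difference, SD 16%: 0.30 / (0.16 × 0.4472) = 4.19, power 0.977 (stated 98%).
- 25% difference, SD 14%: 0.25 / (0.14 × 0.4472) = 3.99, power 0.965 (stated 97%).

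All nine cells of Table 1 agree within 2 points. No gastrin or CgA quantity enters, so the fasting question leaves this figure alone.

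**3. Effect of a common shift**

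Let D be the true drug effect and f the amount by which the shorter fast raises the baseline, both in SDs of the change. The documents give no value for f, so 0 to 1 is an assumed range.

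- Active-arm mean change = D − f
- Placebo-arm mean change = −f
- Difference = (D − f) − (−f) = D

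Simulation of 100,000 trials with 10 per arm:

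| D | f | Active-arm change | Active-arm 95% CI excludes 0 | Between-arm difference | Between-arm t-test rejects |
|---|---|---|---|---|---|
| 0 | 0 | 0.00 | 5% | 0.00 | 5% |
| 0 | 0.25 | −0.25 | 11% | 0.00 | 5% |
| 0 | 0.5 | −0.50 | 29% | 0.00 | 5% |
| 0 | 1 | −1.00 | 80% | 0.00 | 5% |
| 1 | 0 | 1.00 | 80% | 1.00 | 56% |
| 1 | 0.25 | 0.75 | 56% | 1.00 | 56% |
| 1 | 0.5 | 0.50 | 29% | 1.00 | 56% |
| 1 | 1 | 0.00 | 5% | 1.00 | 56% |

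The same holds in units of the overnight value. Suppose the 6-hour baseline is 1.25 times the overnight value and the drug multiplies gastrin by 1.5. The active change is 1.5 − 1.25 = +0.25, the placebo change is 1 − 1.25 = −0.25, and the difference is 0.50, which is the true value.

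**4. Shorter fast in only some patients**

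If a share p in each arm has a shift s, independent of the rest of the change, the mean change moves by −p·s and the variance rises by p(1 − p)s². Take p = 0.5, the share that adds most variance.

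- s = 0.5: mean −0.25, SD √(1 + 0.25 × 0.25) = 1.03.
- s = 1: mean −0.50, SD √(1 + 0.25 × 1) = 1.12.

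Confidence intervals would be about 3% and 12% wider. The expected between-arm difference is still D.

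**5. What the SAP shows**

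SAP 4.3 rules out formal testing. The shell assigned to gastrin and CgA (T_EG2) has values and changes for each arm and no between-arm column. The gastrin and CgA listing has no field for hours since food, and failure to fast is not among the major deviations in SAP 13.2. As specified, a short-fast sample could not be identified afterwards.

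**The case against.** A reader might infer three stronger things, and the documents support none of them.

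- **That fasting is mixed into the drug effect.** The comparison of interest is active versus placebo (SAP 10), both arms follow one schedule, and protocol 13.4 would analyse secondary endpoints by comparing arms. A shift unrelated to arm cancels in expectation. Bias would need a fasting effect that differs by arm, and nothing in the documents suggests one. The SAP also shows the placebo arm, where a shared shift would be visible.
- **That follow-up has no fasting requirement.** The schedule row, 8.5 and 10.3.2 all call for fasting blood. Only the duration, reminder and check are missing.
- **That baseline is in fact taken under a shorter fast.** Six hours can be met by an overnight fast, no endoscopy times are given, and many patients may have fasted overnight. The text permits a shorter fast; it does not impose one.

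It is also fair to say that no meal effect is given for gastrin at 6 hours, that none is argued for CgA, and that these are secondary endpoints in a 20-patient pilot.

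What survives is narrower. The written conditions differ, and the SAP reports these markers as by-arm summaries and plots without a between-arm estimate. Randomisation does not protect a single arm's change. If six hours works as a minimum, fasts will vary between patients, which is the noise problem.

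**Conclusion.** The point holds in a limited form. The fast is defined differently at baseline and on treatment, and its length is left open at follow-up. Each arm's reported change in gastrin and CgA can therefore contain a fasting component, with added noise there and in baseline gastrin as a predictor of the Ki67 change.

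The size is unknown. For an assumed common shift of 0 to 1 SD of the change, the by-arm change is displaced by the full shift. An arm with no true change then has an interval excluding zero in 5% to 80% of trials. The expected active-minus-placebo difference is displaced by nothing, and the Ki67 comparison and its power are not involved.

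This rests on three assumptions: that a shorter fast raises the value, that the shift does not depend on arm, and that change is analysed as a simple difference, as the SAP plans. On a percentage scale the cancellation would not be exact: in the 1.25-fold example the between-arm difference would read 0.50 / 1.25 = 0.40. The inconsistency itself is certain, and the harm is possible but unquantified. It is worth correcting because the correction is cheap.

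**What to change.** **Protocol.** Reconcile 1.2, 8.1 footnote 3, 8.2, 8.5 and 10.3.2 to one fasting condition for the gastrin and CgA samples at all four visits. Which condition to adopt is for the sponsor and investigators. Add a check of the fast at Visit 2 and follow-up, and a reminder in 8.4 before follow-up. Record hours since last food on the CRF at each sample.

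**SAP.** Add hours since last food to the gastrin and CgA listing. In section 15 and its table, report the between-arm difference in change from baseline with its 95% confidence interval at each visit, and make this the main reading of these endpoints. This is estimation, so it does not conflict with the no-testing statement in 4.3, and 11.2 already allows confidence intervals. It needs no new data.

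**Cost.** A few protocol sentences, one CRF field, one listing column and one added display. If the longer of the two fasts is adopted, some patients, including those who combine Visits 1 and 2, may need to fast longer or be booked in the morning.

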8.3 Evaluations during study treatment

Week 6 visit: after 6 weeks of study treatment

The investigator will:

- check that the patient has fasted;
- collect the diary card, and issue a new one;
- check the diary card for compliance with treatment, and for adverse events and concomitant medication;
- collect the study medication bottle and assess compliance;
- do an ECG and vital signs;
- take blood and urine for laboratory safety tests and urine pregnancy testing (pre-menopausal women only);
- take blood samples for fasting serum gastrin, plasma CgA, trough YF476 concentration and serum for storage;
- after taking the fasting blood samples, give the patient their dose of study medication, wait 1 h, then collect blood for assay of peak concentration of YF476;
- issue a new container of study medication, to be taken as before;
- remind the patient to fast before the next visit; and
- remind the patient not to take their study medication at home on the day of the Week 12 visit, but instead to bring their container of study medication with them to the visit, and take their dose at the clinic, after the fasting blood tests and endoscopy.

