1.6 Trial design and methods

Patients will be randomised (1:1 ratio) to receive either 25 mg YF476 or matching placebo. They will attend the clinic 4 or 5 times, and will take up to 18 weeks to complete the trial.

At **Visit 1**, patients will sign the Informed Consent form. Patients will undergo assessment of eligibility, physical examinations, ECG, urine pregnancy test (pre-menopausal women only) and safety tests of blood and urine.

Visit 2 can take place on the same day as visit 1, or up to 2 weeks later. At Visit 2, patients will undergo ECG, safety tests of blood and urine, including urine pregnancy test (pre-menopausal women only), unless Visit 2 is on the same day as Visit 1. All patients will have baseline biomarker assessments, baseline esophagogastroduodenoscopy (EGD) and biopsies. If they meet all the eligibility criteria, they will be given a bottle of study medication (25 mg YF476 or placebo) capsules to take once daily, with breakfast, starting the next day. Patients will complete a diary card throughout the treatment period.

The Week 6 visit will be 6 weeks after starting study treatment. Patients will fast before the visit, and will bring their dose of study medication to the clinic, to take after fasting blood tests. First, patients will have safety tests of blood and urine, ECG, and blood taken for biomarkers and trough YF476 concentration. Patients will then take their study medication, and 1 h afterwards will have blood taken for peak YF476

concentration. Patients will be asked about any adverse events and concomitant medications, and will return their study medication bottle for assessment of compliance. They will receive their next bottle of study medication.

The Week 12 visit will be 12 weeks after starting study treatment. Patients will fast before the visit, and will bring their dose of study medication to the clinic, to take after fasting blood tests. First, patients will have safety tests of blood and urine, ECG, and blood taken for biomarkers and trough YF476 concentration, before undergoing EGD assessments and biopsies. Patients will then take their study medication, and 1 h afterwards will have blood taken for peak YF476 concentration.

Follow-up visit will be 4 weeks after the patients have stopped taking study medication. Patients will have safety tests of blood and urine, ECG, and blood tests for biomarkers. Patients will be asked about any adverse events.

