The pharmacokinetic profile of YF476 varied among the 1996, 2001, 2005 and 2009 capsule formulations. The 2001 and 2005 formulations were crystalline, and the 1996 and 2009 formulations were spray-dried. The spray-dried formulations had the most favourable profile. In a single-dose study of 50–400 mg of the current (2009) formulation of YF476, absorption was rapid, T_{max} was 1.5–2 h, $T_{1/2}$ varied with dose, and C_{max} and AUC_{0-24} were not proportional to dose. $T_{1/2}$ after 100 mg YF476 was about 7 h. Food increased C_{max} and AUC_{0-24} by 1.9 and 1.6-fold, respectively. The absolute bioavailability was about 16% in a study of 100 mg 'cold' YF476 by mouth after fasting and 15 μ g ^{14}C -YF476 intravenously. Protein binding in human serum was about 84%. In a 7-day study of 100 mg YF476 twice daily of the 1996 formulation, YF476 reached steady state by Day 3 and did not accumulate by Day 7. Even though the crystalline formulations were much less bioavailable than the spray-dried formulations, the pharmacodynamic results were still favourable, which suggests that YF476 is a potent gastrin antagonist in man.

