8.4 Evaluations at completion of study treatment

Week 12 visit: after 12 weeks of study treatment

The investigator will:

- check that the patient has fasted;
- collect the diary card;
- check the diary card for compliance with treatment, and for adverse events and concomitant medication;
- collect the study medication bottle and assess compliance;
- do an ECG and vital signs;
- take blood and urine for laboratory safety tests and urine pregnancy testing (pre-menopausal women only);

- take blood samples for fasting serum gastrin, plasma CgA, trough YF476 concentration and serum for storage;
- do an endoscopy and biopsies; and
- after the endoscopy, give the patient their dose of study medication, wait 1 h, then collect blood for assay of peak concentration of YF476.

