## 16.1 Pharmacokinetic Concentration Data

The peak ( $C_{max}$ ) and trough ( $C_{trough}$ ) plasma concentration will be listed, presented graphically and summarised by treatment.

We will produce scatterplots to examine the relationship between peak PK concentrations and plasma CgA concentration or serum gastrin concentration.

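### The only post-dose sample is drawn at 1 h and reported as peak (Cmax), although the protocol's own Tmax is 1.5–2 h, so it cannot be taken as the peak

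*Protocol*

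**What the plan says.** Protocol 1.6 gives the sequence on visit days: "Patients will then take their study medication, and 1 h afterwards will have blood taken for peak YF476" concentration. Footnote 3 to the schedule in protocol 8.1 agrees: "Patients stay for 1 h after dosing for collection of a blood sample for peak YF476 level". Protocol 8.3 tells the investigator at Week 6 to give the dose after the fasting samples, "wait 1 h, then collect blood for assay of peak concentration of YF476". So does protocol 8.4 for Week 12: "after the endoscopy, give the patient their dose of study medication, wait 1 h, then collect blood for assay of peak concentration of YF476". No other post-dose sample is planned at either visit.

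Protocol 3.2.2 gives the pharmacokinetics of the current formulation: "T_{max} was 1.5–2 h". The source is described as follows: "In a single-dose study of 50–400 mg of the current (2009) formulation of YF476". Half-life varied with dose and was about 7 h after 100 mg. Food increased Cmax and AUC0-24 "by 1.9 and 1.6-fold, respectively".

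Peak concentration is a secondary pharmacokinetic endpoint (protocol 9.2, SAP 4.2.2). Protocol 13.2 plans geometric summaries of Cmax and the trough. SAP 16.1 says that the peak, labelled Cmax, and the trough "plasma concentration will be listed, presented graphically and summarised by treatment". It then plots peak concentration against CgA and gastrin. Listing L_PK1 also carries the Cmax label, whereas table template T_PK1 says only Peak.

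**The concern.** A single sample at a fixed time can equal the true maximum or fall below it. Apart from assay error, it cannot exceed it. If it is drawn before most patients peak, the average is understated, and each patient's shortfall depends on how fast that patient absorbs the drug. The label Cmax hides this, because T_PK1 shows neither the sampling time nor whether the dose was taken with food.

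Two things are at stake. One is a stated secondary endpoint. The other is the SAP's exposure-response display, where peak concentration is the only exposure variable. A reader could take the value for a true peak at 25 mg and compare it with Cmax from other studies.

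**Working it through.** **Step 1: times side by side.** The sample is at 1 h and the stated Tmax is 1.5–2 h. The gap is 1.5 − 1 = 0.5 h to 2 − 1 = 1 h. The draw comes at 1/1.5 = 67% to 1/2 = 50% of the time to peak. This comparison needs no model and carries the main conclusion. Tmax is a reported observation, so there is no calculation in the plan to reproduce.

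**Step 2: likely size.** This step needs assumptions that the documents do not supply: a one-compartment model with first-order absorption, a half-life of 7 h (the 100 mg figure) and Tmax as observed at 50–400 mg.

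- Elimination rate: ke = ln 2 / 7 = 0.0990 per h.
- Absorption rate ka is solved from Tmax − lag = ln(ka/ke)/(ka − ke). With no lag, ka = 2.15 per h for Tmax 1.5 h and 1.44 per h for Tmax 2 h.
- Ratio with no lag: C(1 h)/Cmax = [exp(−ke) − exp(−ka)] / [exp(−ke·Tmax) − exp(−ka·Tmax)].
- Tmax 1.5 h: 0.789/0.822 = 0.960. Tmax 2 h: 0.668/0.764 = 0.874.
- Steady state, 24 h interval: each term exp(−k·t) is divided by 1 − exp(−24k), with the same ka, and the ratio is taken to the highest point of the resulting curve.
- With a lag, t is replaced by t − lag.

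| Case (half-life 7 h) | Tmax 1.5 h | Tmax 2 h | Shortfall |
|---|---|---|---|
| Single dose, no lag | 0.960 | 0.874 | 4–13% |
| Steady state, no lag | 0.969 | 0.897 | 3–10% |
| Single dose, lag 0.5 h | 0.903 | 0.743 | 10–26% |
| Steady state, lag 0.5 h | 0.917 | 0.777 | 8–22% |

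**Step 3: sensitivity.** Over assumed half-lives of 3–10 h and lags of 0–0.5 h, the single-dose ratio runs from 0.687 to 0.966, a shortfall of about 3–31%. Sampling is at Weeks 6 and 12 and the protocol describes absorption as rapid, so the steady-state rows and short lags fit the trial better than the extreme cases.

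**The case against.** The strongest objection is that the Tmax may not carry over. It comes from single doses of 50–400 mg, the trial gives 25 mg daily, and protocol 3.2.2 itself says that exposure was not proportional to dose and that half-life varied with it. Some patients could peak at 1 h. This stands. A reader might infer that the reported value is definitely not the peak, but the documents support only that it cannot be assumed to be the peak and is expected to come earlier.

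A second tempting reading is that the trial measures about half the patient's usual peak, since 1/1.9 = 53%. The documents do not establish that. Protocol 1.2 excepts visit days from dosing with breakfast and requires an overnight fast. This implies a clinic dose without food, but no section says so outright. Protocol 6.2 does not treat dosing without food as a deviation, so ordinary exposure is itself mixed. The food effect is not stated to apply at 25 mg. No endpoint claims to measure the usual fed peak, and the fast serves the gastrin and CgA samples and the endoscopy. The food effect is therefore only a caveat: the value may also not reflect exposure on ordinary days.

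It can also be said that the analysis is descriptive, with no formal testing under SAP 4.3, and that the timing loss may be small. Both are fair and limit the weight of the point. They do not justify the label.

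**Conclusion.** The mismatch holds as a matter of timing and labelling. The plan reports as peak and Cmax a single sample drawn 0.5–1 h before the only Tmax that it gives for the current formulation, without justification. Any resulting bias is downward. Its plausible size is about 3–13% without an absorption lag, and up to 22–26% if a 0.5 h lag is assumed. These figures rest on the assumed model, the 7 h half-life and the transfer of Tmax from higher single doses to 25 mg. Only the time comparison is free of assumptions. The point concerns a secondary, descriptive endpoint and the plots built on it. The Ki67 analysis and the power calculation are unaffected.

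**What to change.** Choose one of two options.

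1. **Move the draw.** Take the post-dose sample within the protocol's stated Tmax range of 1.5–2 h at both visits, for patients not yet sampled. Record actual sampling times, and do not pool 1-h samples with later ones. The cost is 30–60 minutes more waiting per visit and a minor amendment. The documents do not show how many patients have already been sampled.
2. **Keep 1 h and rename.** Report a 1-h post-dose concentration, with the prandial state at that dose recorded, and do not call it peak or Cmax. This needs no new samples and works even if sampling has finished.

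Under option 2, relabel consistently:
- Protocol 1.6, 1.9, 4.1, 4.2, 8.1 footnote 3, 8.3, 8.4, 9.2 and 13.2.
- SAP 4.2.2, section 6 footnote 3, 16.1, Table 14.2.1 with template T_PK1, and listing L_PK1.

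Under either option, state the sampling time on the scatterplots against CgA and gastrin, and note that the clinic dose follows an overnight fast. Neither option changes the dose or how it is taken.
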